#### 10.6 Safety Assessments

#### 10.6.1 Adverse Events

The patients will be asked a non-leading question (for example, "how do you feel?", "how have you felt since your last visit?") at each visit, starting at the Screening Visit when the patient signs the *Informed Consent Form*. Adverse events (including worsening of concurrent disorders, new disorders, and pregnancies) either observed by the investigator or reported spontaneously by the patient will be recorded, and the investigator will assess the seriousness and the intensity of each adverse event and its relationship to the IMP. Results from relevant tests and examinations, such as clinical safety laboratory tests, vital signs, MRI, C-SSRS, and ECGs, or their corresponding conditions will also be recorded as adverse events if considered by the investigator to be clinically significant.

See section 11 for further information on adverse events.

## **10.6.2** Clinical Safety Laboratory Tests

The clinical safety laboratory tests are listed in Panel 5.

Panel 5 Clinical Safety Laboratory Tests

Haematology	Liver b	Urine
B-haemoglobin	S-total bilirubin	U-protein (dipstick)
B-erythrocyte count	S-conjugated bilirubin	U-glucose (dipstick)
B-total leucocyte count	S-alkaline phosphatase	U-blood (dipstick)
B-neutrophils a	S-alanine aminotransferase	U-leucocytes (dipstick)
B-eosinophils a	S-aspartate aminotransferase	U-nitrites (dipstick)
B-basophils a	S-gamma-glutamyl transferase	Urine culture
B-lymphocytes a		
B-monocytes a		
B-thrombocyte count		
B-haematocrit		
P-prothrombin time		
S-total tryptase d		
Electrolytes b	Kidney b	Infection
S-sodium	S-creatinine	S-C-reactive protein
S-potassium	S-urea nitrogen	1
S-calcium (total)		
Endocrine and Metabolic b	Lipids b	Pregnancy c
S-albumin	S-low density lipoprotein	hCG tests
B-HbA 1c	S-high density lipoprotein	
S-creatine phosphokinase	S-triglycerides	
	S-cholesterol (total)	
B = blood; hCG = human choriogonadotropin; P = plasma; S = serum; U = urine		

- a Count and % of total leucocytes. If any abnormalities are noted in the complete blood count and/or differential counts, additional workup (ancillary tests) will be performed
- b Clinical chemistry
- c Only for women of childbearing potential, serum hCG test at screening and urine dipstick at later assessments
- d S-total tryptase only to be collected in relation to systemic hypersensitivity reactions (adverse events requiring additional data collection), see section 11.1.3

Blood samples for the clinical safety laboratory tests will be collected as outlined in Panel 2 and Panel 3. The blood sampling and handling procedures are described in the study-specific *Laboratory Specification Manual*.

The blood samples will be analyzed at the central laboratory.

The investigator must review (initial and date) the results of the clinical safety laboratory tests as soon as possible after receipt of those results. Out-of-range values must be interpreted by the investigator as "not clinically significant" or "clinically significant" with a comment concerning the planned follow-up. Tests for clinically significant out-of-range values must be repeated, or an appropriate clinical follow-up must be arranged by the investigator and documented on the laboratory report, until the value has stabilized or until the value has returned to a clinically acceptable value (regardless of relationship to the IMP). A patient with a value that is out-of-range at an EoT or Withdrawal Visit and considered clinically significant must be followed in accordance with usual clinical practice.

If the clinically significant out-of-range clinical safety laboratory test value has not normalized or stabilized or a diagnosis or a reasonable explanation has not been established by the DBP/OLE Safety Follow-up Visit, the investigator must decide whether further follow-up visits are required (this may include an additional medical examination and/or additional blood sampling). Any out-of-range values followed after the last protocol-specified contact with the patient will be documented in the patient's medical records.

For patients that attend the DBP Safety Follow-up Visit before entering the OLE:

Clinically significant out-of-range clinical safety laboratory test values that have not normalized or stabilized or a diagnosis or a reasonable explanation has not been established by the DBP Safety Follow-up Visit should be followed-up on in the OLE by the investigator in accordance with the above.

#### General

Any out-of-range clinical safety laboratory test value considered clinically significant by the investigator must be recorded as an adverse event on an *Adverse Event Form*.

The central laboratory will be notified by the sponsor when the biological samples may be destroyed.

# 10.6.3 Vital Signs

The investigator may appoint a designee to measure vital signs, provided this is permitted according to local regulations and provided the investigator has trained the designee how to measure vital signs. The investigator must take responsibility for reviewing the findings.

Pulse rate and blood pressure will be measured using a standard digital meter in either supine or sitting position immediately prior to start of IMP administration.

Blood pressure and pulse will be measured immediately prior to IMP administration and patients will be monitored immediately after IMP administration inclusive of saline flush ( $\pm 5$  minutes) for immediate drug reactions for a minimum of 2 hours with vital signs taken at the end of the saline flush and then every 30 minutes ( $\pm 5$  minutes) from the end of the saline flush or until stable, whichever is later (applicable only through Visit 12E).

Beginning at Visit 13E, blood pressure and pulse will only be measured immediately prior to and immediately after IMP administration, inclusive of the saline flush (±5 minutes).

Any out-of-range vital sign considered clinically significant by the investigator must be recorded as an adverse event on an *Adverse Event Form* as according to section 11.1.1.

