#### Probable MSA:

#### Criteria for the diagnosis of probable MSA

#### A sporadic, progressive, adult (>30 y)- onset disease characterized by

- Autonomic failure involving urinary incontinence (inability to control the release of urine from the bladder, with erectile dysfunction in males) or an orthostatic decrease of blood pressure within 3 min of standing by at least 30 mm Hg systolic or 15 mm Hg diastolic and
- Poorly levodopa-responsive parkinsonism (bradykinesia with rigidity, tremor, or postural instability) or
- A cerebellar syndrome (gait ataxia with cerebellar dysarthria, limb ataxia, or cerebellar oculomotor dysfunction)

MSA multiple system atrophy.

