16.2 General Methodology for Other safety Data

Unless otherwise specified, tables, graphs, and listings will be based on the APTS.

All tables and graphs will be presented by treatment group.

The denominators for the summaries of a given variable will be based on the number of patients with non-missing values at a given visit or during the assessment period.

Descriptive statistics for the safety variables, both absolute values and changes from baseline, will be presented by visit, separately for each period.

The number and percentage of patients with at least one PCS value at any post-baseline assessment time point will be summarized by variable, separately for each period. All available assessments in each period will be included in the evaluation of PCS values.

For patients with post-baseline PCS values, listings will be provided including all the values for those patients for the variable, with flagging of PCS values and out-of-reference-range values.

For vital signs being measures multiple time during a visit values will be presented graphically within visit over time, where the position will be indicated.

All the adverse events in patients with post-baseline PCS values will be listed by treatment group and patient screening number; the listing will include the PCS value, the assessment date, the change from baseline in PCS value, the preferred term for the adverse event, and start date and stop date of the adverse event. The PCS values and adverse events will be listed in chronological order according to assessment date and the start date of the adverse event

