S-cholesterol total, fasting	CHOL	mmol/L		≥ 6.2
S-triglycerides, non- fasting/unknown	TRIG	mmol/L		≥ 5.65
S-triglycerides, fasting	TRIG	mmol/L		≥4.2
S-LDL cholesterol, non- fasting/unknown	LDL	mmol/L		≥ 5.3
S-LDL cholesterol, fasting	LDL	mmol/L		\geq 4.9
S-HDL cholesterol, non- fasting/unknown	HDL	mmol/L	≤ 0.8	
S-HDL cholesterol, fasting	HDL	mmol/L	≤ 0.9	
Cardiac/Skeletal/Muscle				
S-creatine kinase (total)	СК	U/L		\geq 400 (women)
				≥ 750 (men)
S-creatine kinase MB isoenzyme	CKMB	µg/L		\geq 8.5 or
	CKMBCK	%		\geq 3.5% of total CK
S-lactate dehydrogenase (total)	LDH	IU/L		\geq 750
S-troponin I	TROPONI	µg/L		≥1.5
S-troponin T	TROPONT	μg/L		≥ 0.4
Infection				
S-C-reactive protein	CRP	mg/L		≥25
S-globulin (total)	GLOBUL	g/L	≤15	≥ 55
Urine				

Page 80 of 96

Laboratory Test	CDISC Term	Unit	PCS Low	PCS High
Urinary pH	PH		≤ 4	≥9

S=serum; B=whole blood; U=urine

Table 4	PCS Criteria for Vital Signs, Weight/BMI, and Waist Circumference
---------	-------------------------------------------------------------------

Variable	CDISC Term	Unit	PCS Low	PCS High
Waist circumference	WSTCIR	Cm	decrease $\geq 7\%$	increase $\geq 7\%$
Weight	WEIGHT	Kg	decrease $\geq 7\%$	increase $\geq 7\%$
Body Mass Index	BMI	kg/m2	decrease $\geq 7\%$	increase $\geq 7\%$
Pulse rate, supine/sitting/unknown	PULSE	beats/min	< 50 and decrease ≥ 15	\geq 120 and increase \geq 15
Diastolic blood pressure, supine/sitting/unknown	DIABP	mmHg	≤ 50 and decrease ≥ 15	≥ 105 and increase ≥ 15
Systolic blood pressure, supine/sitting/unknown	SYSBP	mmHg	\leq 90 and decrease \geq 20	≥ 180 and increase ≥ 20
Orthostatic systolic blood pressure	OBP	mmHg	≤ - 30	
Orthostatic pulse rate	OPR	beats/min		≥ 20
Temperature	TEMP	°C	decrease ≥ 2	\geq 38.3 and increase \geq 2

Increase/decrease is relative to the baseline value.

Table 5PCS Criteria for ECG Parameters

ECG Parameter	CDISC Term	Unit	PCS Low	PCS High
Absolute Time Interval				
PR interval	PRAG	Msec		≥ 260
QRS interval	QRSAG	Msec		≥150
QT interval	QTAG	Msec		\geq 500
Derived Time Interval				
Heart rate	EGHRMN	beats/min	< 50 and	\geq 120 and
			decrease ≥ 15	increase ≥ 15
QTcB interval	QTCBAG	Msec	< 300	> 500 or
				increase > 60
QTcF interval	QTCFAG	Msec	< 300	> 500 or
				increase > 60

Increase/decrease is relative to the baseline value.

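### Safety blood pressure and pulse may be read supine or sitting, while the PCS rules and change-from-baseline tables take no account of position

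*Protocol*

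**What the plan says.** **Measurement.** On the reading before the infusion, Protocol 10.6.3 says: "Pulse rate and blood pressure will be measured using a standard digital meter in either supine or sitting position immediately prior to start of IMP". Through Visit 12E patients are then observed "for immediate drug reactions for a minimum of 2 hours with vital signs taken at the end of the saline flush" and every 30 minutes afterwards. No position is given for these later readings, and nothing asks for the same position within a visit or from one visit to the next.

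**PCS rules.** SAP 16.4 takes the criteria from the sponsor's standard list, shown in SAP Appendix V, Table 4. The systolic row is labelled "Systolic blood pressure, supine/sitting/unknown": PCS low is 90 mmHg or less with a decrease of at least 20, and PCS high is 180 or more with an increase of at least 20. Diastolic pressure (50 or less, 105 or more, change of at least 15) and pulse (below 50, 120 or more, change of at least 15) are pooled over position in the same way. The footnote reads: "Increase/decrease is relative to the baseline value". Neither it nor the baseline definition in SAP 3.1.1 mentions position.

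**Use of position.** SAP 16.2 mentions it once, for vital signs measured repeatedly in a visit: "values will be presented graphically within visit over time, where the position will be indicated". The descriptive change tables and PCS summaries in the same section do not use it. A patient counts as PCS once any post-baseline reading in the period qualifies.

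**Orthostatic rows.** Table 4 also has a row "Orthostatic systolic blood pressure" with a limit of -30 mmHg and one for orthostatic pulse with a limit of 20 beats/min. Neither has a change-from-baseline condition.

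**The concern.** A supine baseline followed by a sitting reading can meet the low rule with no change in the patient. A sitting baseline followed by a supine reading can hide a genuine fall. Blood pressure regulation is impaired in this disease: one criterion for probable MSA in Protocol Appendix V is "an orthostatic decrease of blood pressure within 3 min of standing by at least 30 mm Hg systolic or 15 mm Hg diastolic". That criterion concerns standing, but it shows why posture cannot be ignored here.

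At stake is how far the vital-sign safety tables can be read. Because one qualifying reading in a period is enough, small errors per reading accumulate over many visits. The change-from-baseline summaries by visit carry the same noise.

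**Working it through.** The plan states no figure to reproduce. The check sets the rules side by side and then illustrates the size under stated assumptions.

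**1. The rules together.** Position is free (Protocol 10.6.3); change is taken from baseline whatever the position (Table 4); position appears to be available to the analysis (SAP 16.2). Nothing in the plan closes the gap.

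**2. Both directions, worked examples with invented values.**
- Supine baseline 110, sitting follow-up 90, the whole difference postural. 90 ≤ 90 and 110 − 90 = 20 ≥ 20, so the reading is flagged although nothing has changed.
- Supine level 110, postural drop 10, so the sitting baseline is 100. After a true fall of 22 the supine follow-up is 88. 88 ≤ 90, but 100 − 88 = 12 < 20, so it is not flagged. Against a supine baseline, 110 − 88 = 22 and it would be.

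**3. Rate per pair of readings, no drug effect.** Assumptions, none of them in the documents: supine systolic mean 125 (or 140), between-patient SD 18, within-patient SD 10, supine-to-sitting drop with SD 10 cut off at zero, and no drop at all in the zero scenario.

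Baseline = true level + N(0,10). Follow-up = true level − max(0, N(drop,10)) + N(0,10). PCS low = follow-up ≤ 90 and baseline − follow-up ≥ 20.

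| Mean drop (mmHg) | Supine then sitting, mean 125 | Supine then sitting, mean 140 | Sitting then supine, mean 125 |
|---|---|---|---|
| 0 | 1% | 0.2% | 1% |
| 10 | 8% | 3% | 0.4% |
| 20 | 19-20% | 8% | 0.2% |

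With a fixed drop of 10 mmHg instead of a variable one, the 8% becomes 5%.

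**4. Rate per patient, no drug effect.** Same means and SDs at 125, fixed drop, supine baseline, one pre-infusion reading per visit. Panel 2 gives 13 post-baseline site visits to Week 48 (12 four-weekly visits plus Week 6) and 13 + 6 = 19 to Week 72. Share of patients with at least one PCS-low value:

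| Position after baseline | 13 visits | 19 visits |
|---|---|---|
| Supine throughout | 8% | 10% |
| Half sitting, drop 10 | 19% | 23% |
| Half sitting, drop 20 | 41% | 46% |
| Half sitting, drop 30 | 65% | 69% |

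With no drop, mixing positions changes nothing.

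**5. Effect on the comparison.** If both arms mix positions alike, the expected difference between arms is 0. The chance SE of that difference with 20 placebo and 40 active patients is √[p(1−p)(1/20 + 1/40)]. At p = 0.20 it is √(0.16 × 0.075) = 0.110, and at p = 0.40 it is √(0.24 × 0.075) = 0.134. A background rate of 20-40% therefore leaves an SE of about 11 to 13 points.

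**6. The orthostatic rows.** The vital-signs procedure has no standing reading, so it cannot feed them. UMSARS Part III does take supine and standing values, but the SAP treats it as an exploratory efficacy endpoint (4.5.1) and does not link it to Table 4. Two facts stand against linking it as things are. The -30 mmHg limit equals the systolic part of the probable-MSA criterion and has no baseline condition, so it would flag the disease itself. The Part III timing also differs within SAP 24.1.2: Panel 8 has 15 minutes of rest and standing within 10 minutes, while the text has 2 minutes of each. Those two statements must be reconciled.

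**The case against.** The strongest reply is the design. The double-blind period is randomized against placebo, tables are by treatment group, and a PCS count attributes nothing to drug. A reader might infer that posture would be counted as a drug effect throughout the study. For the double-blind comparison the documents do not support that: posture error should be similar in both arms. This stands, and the claim there is limited to false flags and lost sensitivity. It gives no protection in the open-label extension, where everyone receives Lu AF82422, in pre- versus post-infusion comparisons, or in patient listings that set PCS values beside adverse events.

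A reader might also infer that the study has no standing measurement and that the orthostatic rows are a defect in themselves. UMSARS Part III refutes the first. On the second, Table 4 is a sponsor template that also lists waist circumference and temperature, which are in neither schedule of assessments, so an unused row is untidy rather than wrong.

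The diagnostic criterion concerns standing, and the documents give no supine-to-sitting figure. That stands, so every size above is an assumption, and the reverse switch moves the rate the other way.

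There are safeguards: the PCS rules need an absolute limit as well as a change (the simulations include it), investigators record clinically significant vital signs as adverse events, the within-visit graphs show position, and an independent committee reviews unblinded safety data during the double-blind period. These reduce the consequence but do not correct the derived tables.

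**Conclusion.** The point holds as a weakness in measurement and derivation that is cheap to repair. Position is free, and the change-based PCS rules and change-from-baseline summaries do not match on it. The result can be false flags, masked flags or noise, depending on which way position switches. In the double-blind period this costs sensitivity and should not bias the contrast, provided both arms mix positions alike. Misattribution is a risk in the extension, in pre- versus post-infusion readings and in individual listings.

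The size cannot be stated from the documents, which give neither how often position changes nor the supine-to-sitting drop. The per-pair range of about 1% to 20% is for the unfavourable direction only and rests on the assumed means, SDs and drops. If sites already keep position constant, or if sitting barely lowers pressure, the effect is negligible.

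**What to change.** - **Protocol 10.6.3:** add one sentence asking sites to use, and record, the same position for each patient at every safety reading, within and across visits.
- **SAP 16.2 and 16.4:** compute change from baseline and the change-based PCS criteria against a baseline in the same recorded position, and tabulate by position. Keep the all-positions PCS table as well, with flags that rest on mismatched positions marked, so that no low absolute value is lost for want of a matching baseline.
- **SAP Table 4:** state that the orthostatic rows do not apply to safety vital signs, or remove them. Do not fill them from UMSARS Part III as they stand, for the reasons in step 6 of the working; the two Part III timings in SAP 24.1.2 need reconciling in any case.

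The cost is one protocol sentence, a few lines of SAP text and one additional table. The same-position analysis will contain fewer readings, which the retained all-positions table offsets.

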# 10.6.4 Height and Weight

The patient's height will be measured at screening only.

The patient's weight will be measured while wearing light clothing and no shoes.

#### 10.6.5 Electrocardiograms

A standard 12-lead ECG will be recorded using digital ECG recording equipment provided to the investigator or, upon agreement, to an external cardiology centre. The ECGs will be transferred digitally to a central ECG laboratory for evaluation. The investigator will be provided with the results and a cardiological interpretation of the ECG from the central ECG laboratory. Still, the investigator should examine the ECG according to his own judgement for any safety concerns.

The results from the central ECG laboratory will include the RR, PR, QRS, QT, and QTc intervals.

The investigator has the final decision on the interpretation of the ECG results, except for determining exclusion criteria at screening (PR, QRS, and QT interval described in Exclusion Criterion 22 in section 6.3).

Any abnormal ECG result or out-of-range ECG parameter value considered clinically significant by the investigator must be recorded as an adverse event on an *Adverse Event Form*.

## 10.6.6 Physical and Neurological Examinations

The investigator may appoint a designee to be primarily responsible for performing the physical examinations, provided this is permitted according to local regulations. The investigator must take responsibility for reviewing the findings. Whenever possible, the same individual should perform all physical examinations for the patient.

The physical examination (including height at the Screening Visit only) must, at a minimum, include an examination of appearance, extremities, skin, head, neck, eyes, ears, nose, throat, lungs, chest, heart, abdomen, and musculoskeletal system and must be performed by a physician or physician assistant. The examination will include recording of use of feeding tube and/or wheelchair (full-time user – no walking ability; occasional user – limited walking ability).

Genito-urinary system examinations are often not part of routine neurologic practice. For most patients, an external inspection of the genitals should be sufficient. A full gynaecological examination should only be performed if warranted by symptoms or medical history. The renal regions will be examined as part of the abdominal examination.

The neurological examination must be performed by a physician. The neurological examination comprises examination of mental status, cranial nerves, motor system, reflexes, sensory system, coordination, station and gait.

Any abnormal finding or out-of-range value considered clinically significant by the investigator must be recorded as an adverse event on an *Adverse Event Form*.

# 10.6.7 Columbia-Suicide Severity Rating Scale

The C-SSRS is a semi-structured interview developed to systematically assess suicidal ideation and behaviour of patients participating in a clinical study. The C-SSRS has 5 questions addressing suicidal ideation, 5 sub-questions assessing the intensity of ideation, and 4 questions addressing suicidal behaviour. For this study, the following versions of the scale are used: the "Baseline/ Screening" version (lifetime and 6 months assessment) and the "Since last visit" version (for all subsequent visits). It takes approximately 5 to 10 minutes to administer and rate the C-SSRS.

The C-SSRS must be administered in the local language.

The C-SSRS should only be administered by a rater who has adequate experience with clinical studies in CNS indications. The rater should be a clinician, such as a neurologist, geriatrician, psychiatrist, (neuro-) psychologist, or study nurse involved in clinical practice or regularly evaluating patients. For each individual patient, the same certified rater should preferably rate the patient throughout the study. In case of unforeseen circumstances, certified back-up raters should be available throughout the study. Any exceptions must be discussed and approved by Lundbeck and/or its designee.

Rater training and certification will be conducted by the MedAvante-Prophase as agreed with the sponsor. Raters will complete their designated training curriculum based on their initial qualification status and assigned role. Only raters who qualify on study-specific Rater Certification Programme will be authorized to administer the C-SSRS in the study. C-SSRS rater certification will be provided by [name] online training. Documentation of training and certification will be provided to raters for archiving in the investigator TMF. No patient must be rated before the documentation has been archived. New raters joining the study must be trained and certified by using the same certification process. Detailed instructions on how to administer the C-SSRS will be provided to the site in a C-SSRS Guideline.

Any finding on the C-SSRS that is considered clinically significant by the investigator should be reported as an adverse event.

